2.2.7 Withdrawal of Informed Consent

Any data collected in the clinical database after a patient withdraws informed consent from all further participation in the trial, will not be included in the analysis. The date on which a patient withdraws full consent is recorded in the eCRF.

Additional data for which there is a separate informed consent, e.g. PK, [REDACTED] etc., collected in the clinical database without having obtained that consent will not be included in the analysis. These data will be excluded by the presence of the appropriate protocol deviation criterion.

2.2.8 Subgroup of interest

Given the known correlation between PD-L1 expression and response to PD-1 inhibitors in NSCLC, the dosing schedule groups will be analyzed for their post-treatment response rate based on their baseline PD-L1 expression (present/absent), as defined by expression levels <1% or > 1% by immunohistochemistry (IHC) in part 2 of this study.

2.3 Patient disposition, demographics and other baseline characteristics

The FAS will be used for all baseline and demographic summaries and listings unless otherwise specified. Summaries will be reported by treatment group and for all patients and listings will be reported by treatment group, both following the general analysis conventions defined under [Section 2.1](#). No inferential statistics will be provided.

2.3.1 Patient disposition

The number (%) of treated (Part 1 and Part 3) /randomized (Part 2) patients, who are still on treatment, who discontinued the study phases, and the reason for discontinuation will be presented. The screened and not-randomized/not-treated patients and the reasons for screening failure will be listed.

For patient disposition the following summaries, when applicable, will be provided:

- Number (%) of patients who were treated/randomized;
- Number (%) of patients who were not treated / were randomized but not treated;
- Primary reason for not being treated;
- Number (%) of patients who are still on-treatment (based on the ‘End of Treatment Phase’ page not completed);
- Number (%) of patients who discontinued the study treatment phase;
- Primary reason for study treatment phase discontinuation;
- Number (%) of patients who have entered the post-treatment follow-up;
- Number (%) of patients who have discontinued from the post-treatment follow-up;
- Reasons for discontinuation from the post-treatment follow-up;
- Number (%) of patients who have entered the survival follow-up.

2.3.2 Demographics and other baseline characteristics

All demographic and baseline disease characteristics data will be summarized and listed. Categorical data (e.g., gender, age groups: 18- < 65, ≥65 years, race, ethnicity, ECOG performance status, smoking history, others as applicable) will be summarized by frequency counts and percentages; the number and percentage of patients with missing data will be provided. Continuous data (e.g., age, weight, height, body surface area, body mass index) will be summarized by descriptive statistics (N, mean, median, Q1, Q3, standard deviation, minimum and maximum).

BMI and BSA are calculated using the following formulas:

- $BMI [kg/m^2] = weight[kg] / (height[m]**2)$
- $BSA [m^2] = 234.94*(height[cm]**0.422)*(weight[kg]**0.515)/10000$

Diagnosis and extent of cancer

The summary and listing of diagnosis and extent of cancer (disease history) will include primary site of cancer, details of tumor histology/cytology, histologic grade, stage at initial diagnosis, time (in months) since initial diagnosis of primary site, time (in months) from initial diagnosis to first recurrence/progression, time (in months) since most recent relapse/progression, current extent of disease (metastatic sites).

Medical history

A listing of medical history and current medical conditions will be provided by primary system organ class (SOC) and preferred term (PT). Medical history and current medical conditions will be coded using the latest Medical Dictionary for Regulatory Activities (MedDRA) terminology available at the time of reporting.

Protocol deviations

The number (%) of patients with any protocol deviation will be tabulated by deviation category (as specified in the study Edit Check Specifications). All protocol deviations will be listed.

Analysis sets

The number (%) of patients in each analysis set (defined in [Section 2.2](#)) will be summarized and listed.

2.4 Treatments (study treatment, rescue medication, concomitant therapies, compliance)

2.4.1 Study treatment / compliance

The safety set will be used for all summaries and listings of study treatment, the reporting of which will be in accordance to the general analysis conventions defined under [Section 2.1](#) for safety.

Duration of exposure in days, actual cumulative dose, dose intensity (DI), and relative dose intensity (RDI) will be summarized by treatment group, separately for each component of study treatment (NIR178 and PDR001). Duration of exposure will be categorized into time intervals; frequency counts and percentages will be presented for the number (%) of patients in each interval. The number (%) of patients who have dose reductions or interruptions, and the reasons, will be summarized by treatment group.

Patient-level listings of all administered treatment doses with change reasons will be produced.

2.4.1.1 Duration of exposure to study treatment

Duration of exposure (DoE) to study treatment is considered by taking into account the duration of exposure to the investigational or control drug and any combination partner, if applicable:

Duration of exposure to study treatment (*days*) = (last date of exposure to study treatment) – (start date of study treatment) + 1.

Duration of exposure to study drug (*days*) = (last date of exposure to study drug) – (start date of study drug) + 1.

The start/end dates of study drug and study treatment are defined in [Section 2.1.1.2](#).

Part 1, Part 2 and Part 3 (if done):

The last date of exposure to study drug (NIR178 or PDR001) is defined as the end date of that drug + X, where X for a study drug with

- cyclic administration, is *(cycle length - #planned treatment days in a cycle)*
- daily administration, is zero.

Thus (see Table 2-3 for examples),

- For NIR178 continuous BID dosing, the last date of exposure is defined as the last date of administration.
- For PDR001 Q4W dosing, the last date of exposure is defined as the last date of administration + 27 days.
- For NIR178 intermittent regimens in a 28-day cycle with:
 - 2wk-on/2wk-off BID dosing, the last date of exposure is defined as the last date of administration + 14 days.
 - 1wk-on/1wk-off BID dosing (effectively 14-day sub-cycle), the last date of exposure is defined as the last date of administration + 7 days.

The last date of exposure to study treatment is defined as the latest of the last date of exposure for study drugs in the combination.

Note: If the patient died or was lost to follow-up before the derived last date, the last date of exposure to investigational drug is the date of death or the date of last contact, respectively. If the derived last date of exposure goes beyond the data cutoff date, it should be truncated to the date of data cutoff.

Table 2-3 Definition of last date of exposure of study drug

Scenario	Definition of last date of exposure of study drug	Example

Scenario 1: Study drug with a cyclic administration
	
The planned end date of the last cycle in which the last non-zero dose of the investigational drug was last administered.
 
Date of last administration of study treatment in the last cycle + (cycle length - #planned treatment days in a cycle)
	
Example 1: In a once a week administration the cycle length is 7 days. The last date of exposure is the date of last administration in the last cycle + 6 days.
 
Example 2: In a 1 week on and 3 weeks off administration the cycle length is 28 days. The last day of exposure is the date of last administration in the last cycle + 21 days.
 
Example 3: In a 2 weeks on and 2 weeks off administration the cycle length is 28 days. The last day of exposure is the date of last administration in the last cycle + 14 days.

		
Example 4: For an every 2 weeks administration (Q2W) the cycle length is 14 days. The last date of exposure is the date of last administration in the last cycle + 13 days.
 
Example 5: In a 21-day cycle with one or several infusions in the beginning of the cycle, the last date of exposure is the date of last infusion in the last cycle + 20 days.

Scenario 2: Daily administration of the study drug, i.e. BID, QD, and every other day
 
(This includes other intermittent treatment regimens with drug holidays to manage toxicities e.g., 3 weeks on/1 week off, 5 days on/2 days off)
	
Date of last administration of a non-zero dose of the study drug.
	
Example 6: A patient had a permanent discontinuation of the study drug 06Jan2021 after being put on a temporary interruption since 01Jan2021. In this case the last date of exposure is 31Dec2020.
 
Example 7: In a 3 week on and 1 week off administration of a small molecule compound the last date of exposure is the last day of administration of a non-zero dose.
 
Example 8: In a 5 days on and 2 days off administration of a small molecule compound the last date of exposure is the last day of administration of a non-zero dose.

Summaries of duration of exposure of study drugs and study treatment, expressed in weeks (DoE(days)/7) will include categorical summaries (based on clinically meaningful time intervals) and continuous summaries (i.e. mean, standard deviation etc.).

2.4.1.2 Cumulative dose

Cumulative dose of a study treatment is defined as the total dose given during the study treatment exposure and will be summarized for each of the study treatment components.

The **planned cumulative dose** for a study treatment component refers to the total planned dose as per the protocol up to the last date of study drug administration. The planned cumulative dose is not summarized/listed. It is used for relative dose intensity calculations.

The **actual cumulative dose** refers to the total actual dose administered, over the duration for which the patient is on the study treatment as documented in the treatment page eCRF.

For patients who did not take any drug the cumulative dose is by definition equal to zero.

For continuous dosing, the actual cumulative dose is the sum of the non-zero doses recorded over the dosing period and the planned cumulative dose is the planned starting dose summed over the same dosing period.

For intermittent dosing, the actual cumulative dose should be defined based on the days when the patient is assumed to have taken a non-zero dose during dosing periods. For eg., if a patient's duration of exposure is 31 days with assigned dose (X mg, BID) 2wk-on/2wk-off in 28-days dosing period, then the actual cumulative dose is the total dose administered (includes zero or reduced doses) during the initial 14 days of cycle 1 (ceiling of $31/28 = 1$ complete cycle = 2 wk of dosing) and initial 3 days of cycle 2 ($\min(3,14) = 3$). However, the planned cumulative dose is the planned dose for that patient (constant Y mg) cumulated over the dosing days within the duration of exposure.

As the study treatment is a combination agent, there might be patients in the safety set who did not take one component of study treatment and the cumulative dose for that component would be zero.

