1.1.2 Part 2: NIR178+PDR001 schedule optimization

Part 2 of the study will enroll only patients with advanced/metastatic NSCLC who are naïve to prior immunotherapy. Each treatment group characterized by a different dosing schedule of NIR178 160 mg BID will enroll 20 patients. Eligible patients will be randomized in a 1:1:1 fashion to one of the 3 dosing schedules of NIR178 160mg BID (listed below) in combination with PDR001 within a 28-day cycle ([Figure 1-3](#)):

- NIR178 S1: BID continuous
- NIR178 S2: BID 14 days on/14 days off
- NIR178 S3: BID 7 days on/7 days off

Figure 1-33 Alternate NIR178 dosing schedules within one cycle

	Week 1							Week 2							Week 3							Week 4											
Day	1	2	3	4	5	6	7	1	2	3	4	5	6	7	1	2	3	4	5	6	7	1	2	3	4	5	6	7					
NIR178 S1	█	█	█	█	█	█	█	█	█	█	█	█	█	█	█	█	█	█	█	█	█	█	█	█	█	█	█	█	█	█	█	█	█
NIR178 S2	█	█	█	█	█	█	█	█	█	█	█	█	█	█																			
NIR178 S3	█	█	█	█	█	█	█							█	█	█	█	█	█	█	█	█	█	█	█								

The safety, tumor response rates, and tumor immune modulation of the intermittent NIR178 schedules (NIR178 S2 and S3) will be clinically assessed in comparison to that in the continuous schedule (NIR178 S1). Based on cumulative data (including safety, tolerability, ██████████ PK, ██████████) across the three schedules, a dosing schedule may be selected by Novartis for further evaluation in Part 3 after documented discussion with study investigators.

Additionally, correlation between PD-L1 expression and response to PD-1 inhibitors in NSCLC will be further explored in a supportive analysis.

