2.4.1.5 Compliance

Compliance to the study treatment will be summarized in terms of the RDI or percentage of patients who took a predefined percentage of the number of prescribed doses. The predefined RDI categories are < 0.5 , $\geq 0.5 - < 0.75$, $\geq 0.75 - < 0.9$, $\geq 0.9 - < 1.1$ and ≥ 1.1 . The number and proportion of patients falling in each category will be presented.

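### SAP 2.4.1.2 ends planned cumulative dose at two different dates; under its intermittent-dosing sentence, fully compliant S2 and S3 patients who stop mid on-period score an RDI below 1 while S1 patients score 1

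*SAP*

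**What the plan says.** Part 2 randomises NSCLC patients to continuous dosing (S1) or to one of two intermittent schedules: "NIR178 S2: BID 14 days on/14 days off" and "NIR178 S3: BID 7 days on/7 days off".

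Three places in the SAP bear on planned cumulative dose.

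- **Section 2.4.1.2, general definition.** Planned cumulative dose "refers to the total planned dose as per the protocol up to the last date of study drug administration". For continuous dosing, the planned dose is summed over the same period as the actual dose.
- **Section 2.4.1.2, intermittent dosing.** The planned dose is "cumulated over the dosing days within the duration of exposure". Section 2.4.1.1 fixes that duration. For S1, "For NIR178 continuous BID dosing, the last date of exposure is defined as the last date of administration". For S2, with "2wk-on/2wk-off BID dosing, the last date of exposure is defined as the last date of administration + 14 days", the duration runs on past the last dose; for S3 it runs on 7 days. A note shortens it at death, loss to follow-up or data cutoff.
- **Section 2.4.1.3.** The duration used for dose intensity and RDI runs to the end of the last cycle started, regardless of death, last contact or cutoff.

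The worked example in 2.4.1.2 takes a 31-day duration on two weeks on, two weeks off. In the sentence about the actual dose it prints "ceiling of $31/28 = 1$ complete cycle = 2 wk of dosing", followed by 3 days of cycle 2.

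Section 2.4.1.5 then states: "Compliance to the study treatment will be summarized in terms of the RDI", or alternatively by the percentage of patients who took a set share of their prescribed doses. The RDI categories have cut-points at 0.5, 0.75, 0.9 and 1.1.

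**The concern.** The two definitions in 2.4.1.2 agree only when the duration of exposure adds no scheduled dosing day after the last dose. That is always so for S1, whose exposure ends on the last dosing date. It is not so for an S2 or S3 patient who stops part-way through an on-period. The added 14 or 7 days then include on-days that the patient was scheduled to take but had already stopped before. Those days enter the denominator of RDI and nothing enters the numerator.

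A programmer would reasonably follow the sentence written specifically for intermittent dosing. The three randomised schedules would then be scored on different footings. S2 and S3 could appear less compliant than S1 when every patient took every scheduled dose up to stopping. The Protocol's Amendment 6 study status gives 22, 20 and 20 treated patients on S1, S2 and S3, so one misplaced S2 or S3 patient moves an RDI category by 1/20 = 5 percentage points.

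**Working it through.** **The plan's own example.** 31/28 = 1.107, so the floor is 1 and the ceiling is 2. With the floor, dosing days = 14 × 1 + min(31 − 28, 14) = 17, which is the count the example describes. With the ceiling, the printed 1 is not reproduced. At the example's own 31 days, scheduled on-days are also 17, so RDI = 17/17 = 1.00. The example itself shows no shortfall.

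**RDI.** With actual dose A, planned dose P and duration D, RDI = (A/D)/(P/D) = A/P. The duration matters only through the planned days counted in P.

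**S2, duration as in 2.4.1.1.** Fully compliant, last dose on on-day d (1 to 14) of cycle k:
- taken = 14(k − 1) + d
- duration = 28(k − 1) + d + 14, which always covers all 14 on-days of cycle k and never reaches cycle k + 1
- planned = 14k, so RDI = (14(k − 1) + d)/(14k)

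For cycle 2 day 3 (study day 31): taken 17, duration 45, planned 28, RDI = 17/28 = 0.61.

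**S3, duration as in 2.4.1.1.** Last dose on on-day d (1 to 7) of on-week m (two on-weeks per cycle): taken = 7(m − 1) + d, planned = 7m, so RDI = (7(m − 1) + d)/(7m). Cycle 2 day 3 is m = 3, d = 3: 17/21 = 0.81.

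**Window in 2.4.1.3.** Counting to the end of cycle k gives planned = 14k on both schedules. S2 is unchanged. S3 is lower for a stop in the first on-week of a cycle.

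**General definition.** Planned days equal taken days, so RDI = 1.00 on every schedule.

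| Last dose (fully compliant) | Planned to last dose | Planned within 2.4.1.1 duration | Planned within 2.4.1.3 window |
|---|---|---|---|
| S1, any day | 1.00 | 1.00 | – |
| S2, C1D3 | 1.00 | 3/14 = 0.21 | 0.21 |
| S2, C2D3 | 1.00 | 17/28 = 0.61 | 0.61 |
| S2, C4D7 | 1.00 | 49/56 = 0.88 | 0.88 |
| S2, C2D14 | 1.00 | 28/28 = 1.00 | 1.00 |
| S3, C1D3 | 1.00 | 3/7 = 0.43 | 3/14 = 0.21 |
| S3, C1D7 | 1.00 | 7/7 = 1.00 | 7/14 = 0.50 |
| S3, C2D3 | 1.00 | 17/21 = 0.81 | 17/28 = 0.61 |
| S3, C1D21 | 1.00 | 14/14 = 1.00 | 1.00 |

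**How long it lasts, under the 2.4.1.1 durations.** The lowest RDI is at d = 1. On S2 it is 1 − 13/(14k), which is below 0.9 when k < 9.29, so through cycle 9. On S3 it is 1 − 6/(7m), below 0.9 when m < 8.57, so through on-week 8, which is cycle 4.

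**Averages, assuming stops uniform over on-days.** S2: 0.54, 0.77, 0.85, 0.88 and 0.92 for a stop in cycles 1, 2, 3, 4 and 6. S3 (+7 days): 0.79, 0.89 and 0.95 for a stop in on-weeks 2, 4 and 8. The documents give no stopping days, so these are illustrations.

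**The case against.** The strongest reply is that the general definition in 2.4.1.2 governs. It stops the planned dose at the last administration and gives 1.00 for a compliant patient on any schedule. That stands in part: the SAP contradicts itself, and it does not lay down the low RDI as its only rule. But the intermittent sentence is the more specific one, and nothing says which prevails.

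A reader might infer three stronger things that the documents do not support.

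- *That the ceiling slip produces the low RDI.* It sits in the actual-dose sentence, the intended result is printed beside it, and actual dose comes from recorded doses. The SAP does not tell anyone to apply a ceiling to the planned dose.
- *That a 31-day duration is impossible on S2.* Without truncation it would put the last dose on day 17, an off-day. The note in 2.4.1.1 does allow it, for example when a patient is dosed on cycle 2 day 3 and dies that day. Section 2.4.1.3, however, disregards such truncation for RDI.
- *That the schedule comparison on efficacy is biased.* ORR does not use RDI. By Amendment 6, Part 2 had closed and the Protocol (section 2.2) had already named the continuous schedule as preferred, citing clinical efficacy results.

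It is also fair that stops may not be uniform over on-days. Scans are every 8 weeks ± 7 days for the first 40 weeks, near a cycle boundary. An S2 patient who stops on a scan in the preceding off-period has finished the on-period and is unaffected. Finally, 2.4.1.5 allows a percentage-of-doses measure instead of RDI.

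**Conclusion.** The point holds as an internal contradiction with a calculable consequence. If planned dose is counted within the 2.4.1.1 duration, a fully compliant patient who stops before the end of an on-period scores below 1 on S2 and S3, and a compliant S1 patient scores 1.00. The effect is large for stops in roughly the first three cycles on S2 (0.61 at cycle 2 day 3) and smaller on S3. It shrinks with each cycle and is zero for a stop on the last on-day of an on-period; under the 2.4.1.3 window on S3, that is true only of the second on-week of a cycle.

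The figures assume full compliance, no dose change, no truncation, and that dosing days means scheduled on-days. The realised effect is unknown because stopping days are not in the documents. It is confined to descriptive exposure, RDI and compliance summaries for the two intermittent arms. The sponsor should correct it before those tables are read across schedules. The printed ceiling is a separate slip.

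**What to change.** In SAP 2.4.1.2, use one rule for all schedules: planned cumulative dose = planned dose × protocol-scheduled dosing days from first to last administration. Compliant patients then score 1.00 on S1, S2 and S3 for every stopping day.

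In 2.4.1.3, state that the end-of-cycle window does not extend the planned dose, and reconcile that window with the truncation note in 2.4.1.1.

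Replace ceiling with floor, and restate the example so that it follows from 2.4.1.1: S2, last dose on cycle 2 day 3 (study day 31), duration of exposure 45 days, 14 + 3 = 17 planned dosing days.

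The cost is SAP wording and one derivation line. No new data are needed.

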2.4.1.3 Dose intensity and relative dose intensity

Dose intensity (DI) for patients with non-zero duration of exposure is defined as follows:

$DI (mg / day) = \text{Actual Cumulative dose (mg)} / \text{Duration of exposure to study treatment (day)}$.

If for example the dosing unit is mg and the unit of time is a day:

$DI (mg/day) = \text{Actual Cumulative dose (mg)} / \text{Duration of exposure (day)}$
 $= 1200 (mg) / 18 (Day) = 66.7 (mg/day)$

For patients who did not take any drug the DI is by definition equal to zero.

Planned dose intensity (PDI) is defined as follows:

$PDI (mg / day) = \text{Planned Cumulative dose (mg)} / \text{Duration of exposure (day)}$.

Relative dose intensity (RDI) is defined as follows:

$RDI = DI (mg / day) / PDI (mg / day)$.

DI and RDI will be summarized separately for each component of the study treatment by using their respective duration of exposure. For the purposes of reporting, DI and PDI for PDR001 will be expressed in the unit, mg/4week = mg/28 days; whereas, for NIR178, they will continue to be expressed in mg/day. Summary of RDI will include categorical summaries. The RDI categories are < 0.5 , $\geq 0.5 - < 0.75$, $\geq 0.75 - < 0.9$, $\geq 0.9 - < 1.1$ and ≥ 1.1 .

The duration considered for the derivation of the DI and the RDI will be derived from the start date of study treatment to the end of the last cycle initiated, irrespective of date of death, last contact date for withdraw consent and cut-off date.

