1.2 Study objectives, endpoints and estimands

Objectives and related endpoints are described in [Table 1-1](#) below.

Table 1-1 Objectives and related endpoints

Objective	Endpoint
Primary	
Part 1: To evaluate the efficacy of NIR178 and PDR001 combination in patients with selected advanced solid tumors and diffuse large B cell lymphoma (DLBCL)	Overall Response Rate (ORR) by RECIST v1.1 (for solid tumors) or Cheson (for DLBCL) or PCWG3 criteria for mCRPC

Objective	Endpoint
Part 2: To assess the efficacy of continuous and several intermittent dosing schedules of NIR178 in combination with PDR001 in NSCLC	Overall Response Rate (ORR) by RECIST v1.1 (for solid tumors)
Part 3: To evaluate efficacy of intermittent or continuous dosing schedule of NIR178 in one or two selected tumor types	Overall Response Rate (ORR) by RECIST v1.1 (for solid tumors) or Cheson (for DLBCL) or PCWG3 criteria for mCRPC
Secondary	
To assess efficacy of NIR178+PDR001 in select advanced solid tumors and lymphoma	Overall Response rate (ORR) by iRECIST and in addition, for mCRPC, best PSA change from baseline.
To assess efficacy of NIR178+PDR001 in select advanced solid tumors and lymphoma	Disease Control Rate (DCR), duration of response (DoR), Progression Free Survival (PFS), 2 year Overall Survival (OS) rate by RECIST v1.1 and iRECIST (for solid tumors), Cheson (for DLBCL), and PCWG3 criteria for mCRPC
To assess the safety and tolerability of the NIR178 and PDR001 combination using NIR178 hard gelatin capsule and FCT formulation	Frequency, severity and seriousness of AEs, laboratory abnormalities and other safety parameters. Dose interruptions, reductions and dose intensity.
To characterize changes in the immune infiltrate in tumors	Change from baseline in TILs by immunohistochemistry (IHC) (such as CD8)
To characterize the pharmacokinetics (PK) of NIR178, its metabolite NJI765 and PDR001 in combination using hard gelatin capsule and FCT formulation	Plasma concentration time profiles of NIR178, NJI765 and PK parameters. Serum concentration time profiles of PDR001 and PK parameters
To assess immunogenicity of PDR001	Presence and/or concentration of anti-PDR001 antibodies

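### SAP 2.4.1.3 gives conflicting denominators for dose intensity, and the cycle-end rule understates NIR178 dose intensity in fully compliant patients who stop part-way through a cycle

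*SAP*

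**What the plan says.** SAP Table 1-1 lists, among the safety and tolerability endpoints, "Dose interruptions, reductions and dose intensity". Protocol 10.3 defines DI as the cumulative dose actually received over the actual duration of exposure, and SAP section 4 records no change to that.

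SAP 2.4.1.3 then describes the denominator in three ways:

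- The formula line divides by the duration of exposure to study treatment, that is, to the combination. Under SAP 2.4.1.1 the end of that exposure is "defined as the latest of the last date of exposure for study drugs in the combination". The worked example directly below it says only duration of exposure.
- A later sentence states: "DI and RDI will be summarized separately for each component of the study treatment by using their respective duration of exposure".
- The closing paragraph says the duration for both DI and RDI is "derived from the start date of study treatment to the end of the last cycle initiated, irrespective of date of death", and likewise irrespective of last contact and cut-off.

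SAP 2.4.1.1 supplies the drug-level durations. "For NIR178 continuous BID dosing, the last date of exposure is defined as the last date of administration". PDR001 exposure runs 27 days past the last infusion. Intermittent NIR178 exposure runs 14 days (two weeks on, two off) or 7 days (one week on, one off) past the last dose. These are then cut short: "If the patient died or was lost to follow-up before the derived last date", exposure ends at death or last contact, and it never passes the data cut-off.

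**The concern.** The component sentence and the closing paragraph cannot both be followed for continuous NIR178. One stops the clock at the last dose. The other lets it run to the end of the 28-day cycle and switches off the truncation that 2.4.1.1 imposes. No text says which prevails.

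Two programmers working from this SAP could therefore report different NIR178 dose intensities from the same data. Under the cycle-end rule a patient who never missed a tablet appears under-dosed purely because of the day on which treatment stopped. Differences in DI between treatment groups could then partly reflect when patients discontinued rather than how well they tolerated the dose.

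**Working it through.** **The plan's own figure.** SAP 2.4.1.3 gives 1200 mg over 18 days: 1200/18 = 66.7 mg/day. This reproduces, but it does not show which duration the 18 days represent.

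**Inputs.** Cycle length is 28 days (protocol 6.1.1). NIR178 is continuous at 240 mg BID = 480 mg/day, or 160 mg BID = 320 mg/day. PDR001 is 400 mg on day 1 of each cycle.

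**Component rule against cycle-end rule.** For a fully compliant patient whose last NIR178 dose falls on day d of cycle k, with cycle k the last one started:

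- own duration = 28(k-1) + d days
- cycle-end duration = 28k days
- DI ratio (cycle-end to own) = (28(k-1) + d)/(28k)

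At 240 mg BID, own-duration DI is always 480 mg/day. The cycle-end rule gives:

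| Last NIR178 dose | Days dosed | Cycle-end days | Cycle-end DI (mg/day) | Change |
|---|---|---|---|---|
| Cycle 1 day 14 | 14 | 28 | 6720/28 = 240.0 | -50% |
| Cycle 2 day 1 | 29 | 56 | 13920/56 = 248.6 | -48% |
| Cycle 3 day 1 | 57 | 84 | 27360/84 = 325.7 | -32% |
| Cycle 3 day 7 | 63 | 84 | 30240/84 = 360.0 | -25% |
| Cycle 6 day 3 | 143 | 168 | 68640/168 = 408.6 | -15% |

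Earlier in cycle 1 the loss is larger: a stop on day 7 gives 3360/28 = 120 mg/day (-75%). By cycle 12 day 3 it is 1 - 311/336 = 7%. The percentages do not depend on dose.

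**Formula line (combination duration).** Take 160 mg BID with the last NIR178 dose on cycle 2 day 3 (31 × 320 = 9920 mg; own-duration DI 320.0):

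- PDR001 given on cycle 2 day 1, no truncation: 9920/56 = 177.1 mg/day, the same as the cycle-end rule.
- As above, but death on day 33: combination 9920/33 = 300.6; cycle-end still 177.1.
- PDR001 not given in cycle 2: combination 9920/31 = 320.0; cycle-end 177.1.
- PDR001 continued alone through cycle 6 (protocol 6.2.1 allows single-agent continuation): last infusion on day 141, plus 27 = day 168. Both give 9920/168 = 59.0, or 18% of 320. For the cycle-end rule this counts PDR001-only cycles as cycles started.

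**RDI.** When DI and planned DI share a denominator it cancels: 9920/9920 = 1.00 on 31 or 56 days. Only a mixture moves it: (9920/56)/(9920/31) = 0.55.

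**Effect of truncation on cyclic dosing.**

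- PDR001: one 400 mg infusion, death on day 14. Truncated: 400/14 × 28 = 800 mg/4 weeks. Untruncated: 400/28 × 28 = 400 mg/4 weeks.
- NIR178 160 mg BID, two weeks on and two off: all 14 dosing days taken (4480 mg), death on day 14. Truncated: 4480/14 = 320 mg/day. Over the full 28 days: 160 mg/day, which is what that schedule delivers.

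**The case against.** The case for leaving this as a minor wording matter has real force. The DI formula is restated in the worked example without reference to study treatment, the component sentence follows, and the protocol's wording fits a drug-level duration. Read together, these largely settle that the combination's duration is not the intended denominator. A reader might infer three equally live rules, two of which halve NIR178 DI. The documents do not support that: the formula line is loose wording, and its effect depends on PDR001 being given in the last cycle and on no truncation.

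A reader might also infer that RDI and the compliance categories in SAP 2.4.1.5 are distorted, since the DI formula names the treatment duration and the planned-DI formula does not. That is not supported either. The component sentence and the closing paragraph each cover DI and RDI together, and nothing directs mixing durations.

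Finally, the untruncated rule has a purpose. Deleting it and truncating everything would double PDR001 DI in the example above. DI is also purely descriptive: no test, futility rule or dose decision in the documents uses it.

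All of this stands. It does not remove the conflict between the component sentence and the closing paragraph for continuous NIR178.

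**Conclusion.** The concern holds as a conflict between two stated rules for a named secondary measure. For continuous NIR178 the cycle-end rule understates DI in a fully compliant patient who stops mid-cycle: about 50% for a stop on day 14 of cycle 1, 48% on day 1 of cycle 2, 25 to 32% in the first week of cycle 3, and about 15% early in cycle 6. A general statement that DI is halved would go too far.

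These are single-patient figures assuming full compliance and, except where stated, no further cycle after the one in which NIR178 stops. The documents give no distribution of stop days, so the effect on group summaries is unknown. RDI and compliance stand provided DI and planned DI share a denominator. The primary ORR analysis is untouched. Severity is low, but as written the reported DI cannot be reproduced with certainty.

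**What to change.** In SAP 2.4.1.3:

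1. Change the DI formula so that it divides by the component's own duration of exposure, and state that planned DI uses the identical denominator.
2. Restrict the closing paragraph so that it does not apply to continuous NIR178, whose denominator ends at the last administration.
3. For cyclic dosing, use the planned exposure interval already set out in 2.4.1.1 (last PDR001 infusion plus 27 days; last intermittent NIR178 dose plus 14 or 7 days). For the DI calculation only, do not truncate it at death, last contact or cut-off. The truncated duration can still be reported as duration of exposure.

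The cost is a few lines of SAP text and one derivation in the dataset specifications. No new data are needed.
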